6.0 Study Procedures

The procedure studies will be as followed:

- Once non-operative management is deemed appropriate based on review of imaging and shared decision making with the family, eligible patients will be offered study participation during initial presentation at outpatient clinic visit (about 3-7 days post-injury). At the initial visit:
 - Standard or care X-rays will be reviewed
 - As part of standard of care a cast will be applied (or overwrapped with fiberglass)
 - Some participants will be provided an activity monitoring, based on availability, to be worn on the uninjured wrist or ankle consistent with manufacturers recommendations for the duration of casting treatment.
 - Participants will be randomized into restricted activity vs full activity groups and be read a respective standardized script regarding activity limitations. The same guidance will also be provided in the after visit summary (AVS).
 - Basic data will be collected including patient age, sex, BMI, initial displacement measurements, and other pertinent fracture characteristics easily obtainable from review of present radiographs.
- Patients will follow up at standard of care 1-2 week intervals for alignment checks. At these visits:
 - If the participants was provided a tracker, data from the monitoring devices will be imported with only a study id and date of birth to identify the patient. All data on the device will be deleted when information is imported.
 - Repeat standard of care x-rays will be obtained to assess for loss of reduction (defined as any change in angulation >10 degrees compared to initial reduction).
 - Incidence of complications such as unplanned cast changes, excessive skin irritation, cast wedging, loss of reduction, and operative management will be recorded.
 - For all enrolled patients, regardless of use of activity monitoring device, a validated Pediatric Activity Survey will be provided at follow-up appointments.
- Following all data collection, patient, survey, and activity tracker data will be analyzed

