Appendix A Study Procedure Calendar

1.0 Background

Pediatric forearm fractures are extremely common, accounting for up to 40% of all pediatric fractures and consequently, the financial healthcare burden is large. The rate of displacement following closed reduction with casting/splinting of such fractures is high, varying between 21-39% (Meta-analysis Sengab). Consequences of fracture displacement include multiple adverse complications such as repeat sedation and fracture manipulation causing pain and distress, urgent or unplanned surgical interventions, and potentially malunion of the fracture. In addition to the morbidity of suboptimal fracture healing, there are significant functional consequences that could result due to fracture malunion. Previous studies have evaluated risk factors for forearm fracture displacement following closed reduction including initial displacement, cast index, and BMI however, little work has been done to evaluate the influence activity plays on the displacement/malunion of these fractures. As a result, this leads to inconsistent and nebulous recommendations provided to families regarding activity restrictions after closed treatment of fractures (i.e. non-surgical treatment). One can find significant variability in activity recommendations based on practices and individual provider preferences. Several studies have been conducted in other pediatric patient population to assess activity levels of children with various comorbidities. The purpose of this study is to evaluate the effect of activity on fracture displacement using and actigraph activity monitoring device. This device is externally applied and is an FDA approved activity monitoring devices with an extensive research background.

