2.0 Rationale and Specific Aims

Rate of displacement following cast/splint application has been studied and varies between 21-39% based on the meta-analysis by Sengab et al. This randomized pilot study will include roughly 50-100 patients and will be completed in approximately 1 year with preliminary results available at that time. Between the 8 physicians and 4 nurse practitioners on staff within the pediatric orthopaedics department, approximately 20 patients weekly are seen who would meet eligibility for study participation. Assuming a 10% successful recruitment rate, it would require 6 months to recruit the desired number of participants. Eligible patients will be offered study inclusion during the initial outpatient clinic visit. These patients typically present to the clinic 3-7 days following injury.

The primary aim of this study is to determine whether activity influences loss of reduction of forearm fractures. Secondary aims of this study may provide insight to many other related questions as seen below:

- Does increased activity lead to more complications.
- Do instructions given to families influence activity level and do patients/families accurately report activity levels?
- Does activity level affect recovery length time of forearm fractures based on x-ray findings?

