7.0 Risks

Given that there is not standardized or accepted activity recommendation for these patients, this study will not put these patients at increased risk of further injury. Further, the activity recommendations for the “unrestricted activity” group has common-sense exceptions on what the patient is allowed to do to prevent further injury such as avoidance of high risk situations such as contact sports. The devices are safe and usually well tolerated and have been validated for use in children. Minor possibility of skin irritation from the activity tracker due to chronic use however the device can easily be taken off if this is a problem. There are no other identifiable risks pertaining to the activity monitors or the activity restriction guidelines for providers, patients, or families.

Because patient data is being collected there is a slight risk of a breach of confidentiality. To reduce this risk, this study will utilize the REDCap platform for data collection and management. This project will utilize the REDCap platform for data collection and management. Project team

members listed as Key Study Personnel with existing electronic health record (EHR) system access rights may also be granted use of REDCap Clinical Data Interoperability Services (CDIS) tools. These tools are designed to enable transfer of relevant study-related data from the Vanderbilt Research Derivative and/or directly from the EHR into REDCap.

Only research personnel will have access to the patient's study information to ensure confidentiality. Any data sent to non-key study personnel for statistical analysis will be deidentified (dates will be shifted using a REDCap feature. The data obtained and stored in Redcap will only be accessible by research personnel. Any physical study forms (ex. Consent documents, surveys) will be kept in a locked cabinet in the principal investigator's office]. All study data will be maintained for 6 years following study completion. Following this 6 year period, the Redcap database will be archived, electronic files will be permanently deleted and all physical study forms will be disposed of in shred-it confidentiality bins provided by VUMC. This research may benefit patients in the future by allowing surgeons to provide more appropriate, evidence-based counseling to patients and families to prevent further injury/complication

8.0 Reporting of Adverse Events or Unanticipated Problems involving Risk to Participants or Others

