9.0 Study Withdrawal/Discontinuation

Patients will be asked to contact study personnel if they decide they no longer want to participate in the study. Once a patient has withdrawn their consent, no further study data will be collected on them, and all data that has been collected up until the point their consent was rescinded will be destroyed.

If the patient refuses or withdraws from the study, they will continue receive routine care with normal follow up appointments consistent with standard practice.

Patients may be withdrawn from the study for lack of compliance wearing the activity monitor.

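### The activity monitor may be worn on the wrist or the ankle, and the protocol neither chooses one site nor requires the site to be recorded, so device-based activity analyses can carry avoidable error

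*Protocol*

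**What the plan says.** Section 1.0 makes the device the means to the study's end: "The purpose of this study is to evaluate the effect of activity on fracture displacement using and actigraph activity monitoring device". Section 2.0 has activity as the exposure in the primary aim and adds a secondary question that needs a measured reference: "Do instructions given to families influence activity level and do patients/families accurately report activity levels".

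Section 6.0 says who gets a device: "Some participants will be provided an activity monitoring, based on availability". It then says where it goes: "to be worn on the uninjured wrist or ankle consistent with manufacturers recommendations". The sentence ends by saying that the device is worn throughout cast treatment. At follow-up visits the readings are imported, and "All data on the device will be deleted when information is imported".

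A second activity measure does not depend on the device: "For all enrolled patients, regardless of use of activity monitoring device, a validated Pediatric Activity Survey will be provided at follow-up appointments".

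No section picks one of the two sites. The baseline items listed in section 6.0 do not include wear site, although that list is open-ended. The manufacturer's recommendations are cited but not reproduced.

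**The concern.** A motion sensor records the movement of the limb that carries it. Wrist and ankle readings are therefore not directly comparable unless site is allowed for. This is a reviewer's inference; the protocol does not discuss it.

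If some children wear the device on the wrist and others on the ankle, part of the spread in measured activity reflects site and not activity. Two analyses are exposed. The relation of measured activity to loss of reduction would be diluted. In the check of family reports against the device, a site difference could look like misreporting.

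The choice has to be made in the protocol or on the data form. A statistical analysis plan can adjust for site only if someone wrote the site down during the trial.

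**Working it through.** **Check of the text.** Three questions were put to the protocol.

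1. Is one site chosen? No. Section 6.0 names two, and no other section narrows them. The reference to the manufacturer qualifies the pair.
2. Is the site to be recorded? Not stated. Neither the listed baseline items nor the description of the import names it. A form that is not shown may hold it.
3. Is the site constant within a patient? Not stated outright. Wear throughout cast treatment can be read as one placement per patient, but the sentence does not say so.

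**Illustration of size.** The protocol gives no figure on this point, so there is none to reproduce. Every input below is assumed: a ratio r between mean readings at the two sites (1.25, 1.5 or 2); a between-patient CV within a site (30%, 40% or 60%); and a share p of patients at the less common site (0.10, 0.25 or 0.50). Site is taken as unrelated to activity and ignored in the analysis.

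Within-site variance on the log scale is v = ln(1 + CV²), which gives 0.0862, 0.1484 and 0.3075 for the three CVs. Mixing sites adds p(1 − p)(ln r)², so the variance is multiplied by

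1 + p(1 − p)(ln r)² / v.

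Central case, r = 1.5 and CV 40%: (ln 1.5)² = 0.1644. At p = 0.50 the factor is 1 + 0.25 × 0.1644 / 0.1484 = 1.277. A true correlation of 0.60 between reported and measured activity is divided by the square root of the factor: 0.60 / √1.277 = 0.531.

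| Site mix | Factor, central case | 0.60 reads as | Variance increase over all assumed r and CV |
|---|---|---|---|
| one site | 1.00 | 0.60 | 0% |
| 90:10 | 1.100 | 0.572 | 1.5% to 50% |
| 75:25 | 1.208 | 0.546 | 3% to 105% |
| 50:50 | 1.277 | 0.531 | 4% to 139% |

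The low end of each range is r = 1.25 with CV 60%; the high end is r = 2 with CV 30%.

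A second parameterisation, also assumed, gives the same picture. With a site offset of d within-site SDs, reliability is 1 / (1 + p(1 − p)d²). For d from 0.5 to 2 and p from 0.1 to 0.5 it runs from 0.98 down to 0.50, so a correlation is multiplied by 0.99 to 0.71.

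**Cost of adjusting when site is known.** With a constant ratio between sites, a partial correlation spends one degree of freedom: 1 − (n − 3)/(n − 2) = 1/(n − 2). That is 1/23 = 4.3% for 25 monitored patients and 1/48 = 2.1% for 50 (assumed counts).

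The calculation covers mixing between patients only. A change of site within a patient was not quantified.

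**The case against.** The strongest reply is that this is missing detail and not a wrong rule. Placement is limited to two sites, the injured limb is avoided, and the manufacturer's recommendations govern. Those recommendations may favour one site, and a data form may already hold a site field. This stands as a limit on certainty: the document does not show that site goes unrecorded or that sites are mixed in practice. It does not remove the point, because the rule as written permits both sites, and guidance on wearing the device at each would not make patients comparable.

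The size rests wholly on assumptions and runs from nothing to more than a doubling of variance. That also stands, so the figures illustrate and do not rank the issue.

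Three stronger readings are tempting, and the document does not support them.

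- A reader might infer that clearing the device destroys the site information. The readings are imported first, nothing says that the device stores its wear site, and families are present at the visit and could be asked.
- A reader might infer that the device will move between limbs because section 7.0 says "however the device can easily be taken off if this is a problem". That remark is about removal for skin irritation and does not mention moving it, and wear throughout casting may imply a single placement.
- A reader might infer that the trial's main comparison is compromised. Loss of reduction by assigned group is read from x-rays, and the survey goes to every enrolled patient. Neither depends on wear site.

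**Conclusion.** The point holds as a cheap improvement, with medium confidence. Section 6.0 permits two wear sites without choosing between them or requiring a record, so device-based analyses can mix non-comparable readings. Its reach is the monitored subset and the two uses of device data named above.

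The size of the error is unknown. It is zero if one site is used in practice. Under the central assumptions it is modest: a 10% to 28% rise in log-scale variance, and a correlation of 0.60 read as 0.57 to 0.53. These values depend on the assumed ratio, CV and site mix, on site being unrelated to activity, and on site being ignored in the analysis. If site is recorded and adjusted for, nearly all of the loss is avoidable.

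**What to change.** In section 6.0, name one wear site for all monitored patients, consistent with the manufacturer's recommendations, and state that it is kept for the whole casting period. Record site and side when the device is issued and again at each download. Allow the other site as a recorded exception. If exceptions occur, adjust or stratify the device analyses by site.

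The exception should count as wearing the monitor. Section 9.0 says "Patients may be withdrawn from the study for lack of compliance wearing the activity monitor", and without that wording a child who cannot tolerate the chosen site could be lost from the study.

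The cost is a sentence or two of protocol text and one data field, with no extra devices or visits. The downside is that a few children may not tolerate the fixed site, which the recorded exception covers.

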4.0 Inclusion/Exclusion Criteria

Included in the study will be patients ages 8-18 years old with fractures of radius and/or ulnar shaft or distal radius fracture. Specifically the following fractures will be included:

- Isolated Distal Radius Metaphyseal Fx (with or without ulna styloid)
- Distal Third (<4 cm from physis) Radius and Ulna fracture (i.e. without obvious physeal involvement)
- Insolated Radial Shaft Fracture (diaphyseal)
- Radial and Ulna Shaft Fracture (diaphyseal)

Exclusion Criteria include:

- Initial presentation >7 days from the time of injury
- Pathologic fracture
- Any patient with metabolic bone disease (ex. Osteoporosis, skeletal dysplasias)
- Any patient with known bone fragility condition (ex. Osteogenesis imperfecta)
- If operative treatment is required at initial presentation

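### The primary-aim outcome is measured from the initial reduction, but eligible patients need not have had one, and the reference film is neither named nor tied to the day of assignment.

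*Protocol*

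**What the plan says.** Protocol Section 2.0 states the aim: "The primary aim of this study is to determine whether activity influences loss of reduction of forearm fractures". Section 6.0 supplies the only definition of that outcome: "defined as any change in angulation >10 degrees compared to initial reduction". It names no film and no date.

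Section 4.0 sets eligibility by age and fracture site: "patients ages 8-18 years old with fractures of radius and/or ulnar shaft or distal radius fracture". The exclusions are late presentation, pathologic fracture, metabolic bone disease, bone fragility, and surgery: "If operative treatment is required at initial presentation". Neither displacement nor a closed reduction is an entry condition.

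On timing, Section 2.0 says: "These patients typically present to the clinic 3-7 days following injury". Section 6.0 places enrolment, group assignment and the reading of the script at that first clinic visit. Existing x-rays are reviewed and a cast is applied or overwrapped. No reduction is listed for the visit, and no film is required on that day. Section 6.0 also has displacement measured at baseline, but does not link that measurement to the outcome.

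**The concern.** There are two separate problems.

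1. **Coverage.** The definition presupposes a reduction that the entry criteria do not. A fracture managed in a cast without reduction is eligible, yet the rule gives nothing to compare its later films with. Each reader must then choose a reference, or the patient has no primary-aim outcome.
2. **Time zero.** The randomised comparison starts when the script is read. If the reference film is older than that, change that had already happened is counted as an outcome although the advice could not have caused it. Section 4.0 removes early losses that need surgery at presentation, but not those still managed in a cast.

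The wording also gives no direction of change, although the term loss implies worsening. That is a small drafting point.

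**Working it through.** The protocol has no sample-size calculation to reproduce. The check is a reading of the text, followed by an illustration of size.

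**Step 1: coverage.** Set Section 4.0 beside Section 6.0. No entry criterion requires reduction. Section 1.0 frames the question as "activity restrictions after closed treatment of fractures (i.e. non-surgical treatment"), which is wider than reduced fractures. The definition in Section 6.0 applies only to reduced ones. This gap needs no numbers.

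**Step 2: timing.** The assignment visit lists no reduction, and overwrapping implies that some patients arrive already immobilised. So reductions probably precede assignment. This is an inference, because the protocol does not date them.

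**Step 3: size of the early-drift effect, if the inference is right.** Inputs:
- From the protocol: "The rate of displacement following closed reduction with casting/splinting of such fractures is high, varying between 21-39" per cent (Section 1.0), and "This randomized pilot study will include roughly 50-100 patients" (Section 2.0), so at most 50 per arm.
- Assumed: total restricted-arm risk T = 0.30 (inside the cited range); full activity doubles the post-assignment risk; a share f of restricted-arm losses precedes assignment and is equal in both arms; two-sided 5% test.

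With pre = f × T:
- Definition as written: restricted T; full activity pre + 2(T − pre).
- Reference at assignment, everyone kept, no further loss after an early one: T − pre against 2(T − pre).

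Power = Φ{[d − 1.96√(2p̄(1−p̄)/n)] / √[(p₁(1−p₁)+p₂(1−p₂))/n]}, where d is the risk difference and p̄ the mean risk.

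Example, 0.30 vs 0.50, n = 50: p̄ = 0.40; 1.96 × √0.0096 = 0.192; √0.0092 = 0.0959; (0.200 − 0.192)/0.0959 = 0.083; Φ = 0.533.

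| f | pre | As written | RR | Difference | Power | Assignment reference | RR | Difference | Power |
|---|---|---|---|---|---|---|---|---|---|
| 0.20 | 0.06 | 0.30 vs 0.54 | 1.80 | 0.24 | 69% | 0.24 vs 0.48 | 2.0 | 0.24 | 71% |
| 1/3 | 0.10 | 0.30 vs 0.50 | 1.67 | 0.20 | 53% | 0.20 vs 0.40 | 2.0 | 0.20 | 59% |
| 0.50 | 0.15 | 0.30 vs 0.45 | 1.50 | 0.15 | 34% | 0.15 vs 0.30 | 2.0 | 0.15 | 43% |

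The ratio moves and the difference does not. Power changes only because the lower event rates have smaller variance. If early losses are instead left out of the denominator (47, 45 or 42.5 per arm), power is 73%, 61% or 45%. If half the patients have no film at the enrolment visit, half of pre stays in both arms. The comparisons become 0.27 vs 0.51, 0.25 vs 0.45 and 0.225 vs 0.375, with power 70%, 56% and 37%.

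**Step 4: unreduced fractures.** Let u be their share (assumed), with 0.30 vs 0.50 in reduced fractures and 100 enrolled.

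| u | Left out: n per arm | Power | Kept, never displacing | Power |
|---|---|---|---|---|
| 10% | 45 | 49% | 0.27 vs 0.45 | 47% |
| 25% | 37.5 | 42% | 0.225 vs 0.375 | 37% |
| 50% | 25 | 30% | 0.15 vs 0.25 | 24% |

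If unreduced fractures displace as often as reduced ones, and respond alike, keeping them returns power to 53%. Whether inclusion helps or hurts depends on a rate that the protocol does not give.

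**The case against.** The best defence is that a clinician would read the reference as the alignment accepted at the first clinic visit. Films are reviewed there, baseline displacement is measured from the films at hand, and follow-up films are described as repeats. On that reading little or no early drift is counted. The reading is reasonable, but the protocol does not state it. The films reviewed may themselves predate the visit, and two competent readers could choose different ones.

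A second defence is that the aim and the cited 21-39% both concern reduced fractures, so limiting the outcome, or entry, to those would be an equally legitimate repair. That stands as an alternative, but the present text does neither.

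A third is that this is a pilot and a few points of power under assumed shares show little harm. That also largely stands.

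Three stronger readings are tempting, and the documents support none of them:
- **That the trial does count pre-assignment drift.** The reduction is not dated, so this is conditional.
- **That early drift biases the comparison in one direction.** With comparable groups it falls on both arms alike and leaves the risk difference essentially unchanged. Section 5.0 assigns by odd or even date, which is predictable, so comparability is assumed and not guaranteed. Nothing shows an imbalance.
- **That a common reference recovers power by bringing in unreduced fractures.** Step 4 shows that it can lower power.

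**Conclusion.** The point holds in a limited form. It is certain from the text that the outcome has no stated reference for eligible fractures that were never reduced, and that the reference film is not named or tied to assignment for the rest. This goes beyond detail that could be left to a statistical analysis plan, because the protocol itself fixes a reference that does not fit its own population or the start of its comparison.

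The consequence of early drift is conditional on reductions preceding the clinic visit, and it is modest: attenuation of the risk ratio and some added noise. The power cost in the illustration is about 2 to 10 percentage points at 50 per arm with everyone kept (69% vs 71%, up to 34% vs 43%), and it is small if early drift is rare. The shares f and u, the doubling of risk and the 30% base risk are assumptions. The case for correction rests on having one applicable outcome rule, not on the power figures.

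**What to change.** Keep the 10-degree threshold. Define the outcome as worsening of angulation by more than 10 degrees from the most recent film taken on or before the day of assignment (the enrolment-visit film where there is one) to any later standard-of-care film. Use the same rule for every participant, reduced or not. Record at baseline whether the fracture was reduced and the date of the reference film. Report results in reduced fractures, including change from the initial reduction, as a secondary analysis.

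The cost is one rewritten definition, two baseline fields and one secondary analysis. No new films are needed, because the rule uses films that already exist. The downsides are somewhat fewer events, less comparability of the main outcome with the cited 21-39%, and some residual early drift where no film was taken at the enrolment visit.

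### Survey and alignment x-ray share a follow-up visit with no fixed order, so activity may be reported after the family learns the fracture displaced

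*Protocol*

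**What the plan says.** Protocol section 6.0 (Study Procedures) introduces the follow-up visits with "Patients will follow up at standard of care 1-2 week intervals for alignment checks. At these visits" and puts four items under that heading: import of tracker data where a tracker was given, x-rays, recording of complications, and the activity survey. The x-ray item reads "Repeat standard of care x-rays will be obtained to assess for loss of reduction". The survey item covers all enrolled patients, with or without a monitor: "a validated Pediatric Activity Survey will be provided at follow-up appointments". No sequence within the visit is stated, and nothing keeps the x-ray result from the family until the survey is done.

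Three other statements bear on the point:

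- Section 2.0: "The primary aim of this study is to determine whether activity influences loss of reduction of forearm fractures".
- Section 2.0, among the secondary aims: "do patients/families accurately report activity levels".
- Section 6.0, on monitors: "Some participants will be provided an activity monitoring, based on availability".

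**The concern.** In the primary aim, activity is the exposure and loss of reduction is the outcome. For any child without a monitor, the survey is the only record of what the child actually did. If the survey is answered after the film has been discussed, the exposure is measured with knowledge of the outcome.

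The families have reason to react. Both scripts in Appendix A say it is unknown whether staying active in a cast affects the risk of complications, so every family knows the question under study. The restricted group has also been asked to hold back. A family just told that the fracture has moved may search its memory for a cause and report more activity, or may play down activity that went against the advice. In either case the reporting error differs between displaced and non-displaced children.

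Two results are at stake. A survey-based association between activity and displacement could be created or hidden by the timing of the questionnaire. And the aim on reporting accuracy would mix ordinary recall error with a reaction to bad news.

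**Working it through.** **Text check.** The protocol gives no figure to reproduce here, so the first step is to set the statements side by side.

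| Element | Where | What is fixed |
|---|---|---|
| X-ray for loss of reduction | Section 6.0 | At the follow-up visits |
| Activity survey, all patients | Section 6.0 | At the same visits |
| Order of the two | – | Not stated |
| Monitor | Section 6.0 | Some participants only |

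The protocol therefore permits the survey to follow disclosure of the result. It does not require that.

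**Illustration of size.** Inputs from the protocol:

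- Displacement rate, section 1.0: "The rate of displacement following closed reduction with casting/splinting of such fractures is high, varying between 21-39" percent. The illustration takes p = 0.30, inside that range, and then checks both ends.
- Sample size, section 2.0: "This randomized pilot study will include roughly 50-100 patients". Both ends are used.

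Assumptions not in the protocol: a two-sided 5% test comparing mean reported activity in displaced and non-displaced children; no true association; every child contributing a survey report; and every displaced child's report shifted in the same direction by d standard deviations.

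The standard error of the standardized mean difference is √(1/(Np) + 1/(N(1−p))), so the noncentrality is

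λ = d × √(N p (1−p)),

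and the false-positive rate is Φ(λ − 1.96) + Φ(−λ − 1.96).

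- N = 100, p = 0.30: 30 displaced, 70 not; √(100 × 0.30 × 0.70) = √21 = 4.583.
- N = 50, p = 0.30: 15 displaced, 35 not; √(50 × 0.30 × 0.70) = √10.5 = 3.240.

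| d (SD, assumed) | λ, N=100 | False-positive rate, N=100 | λ, N=50 | False-positive rate, N=50 |
|---|---|---|---|---|
| 0 | 0 | 0.050 | 0 | 0.050 |
| 0.2 | 0.917 | 0.150 | 0.648 | 0.099 |
| 0.3 | 1.375 | 0.280 | 0.972 | 0.163 |
| 0.5 | 2.291 | 0.630 | 1.620 | 0.367 |

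Across the protocol's displacement range (21% to 39%), a 0.5 SD shift gives 53% to 68% at N = 100 and 30% to 41% at N = 50. A 0.25 SD shift gives 18% to 23% and 11% to 14%. The last pair also indicates what happens if only about half of the displaced families shift by 0.5 SD, since the mean shift is then 0.5 × 0.5 = 0.25 SD (ignoring the small change in variance).

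**The case against.** **List order is not procedure order.** The survey stands below the x-ray in the list, and a reader might infer that the protocol places it after the film. It does not. The items are simply what happens at these visits, and the list for the initial visit is not evidently chronological either: randomization is written after cast application and monitor provision. This objection stands, and the point rests only on the order being left open.

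**The primary aim survives without the survey.** A reader might infer that the whole trial is compromised. The documents do not support that. Comparing loss of reduction by randomized group makes no use of the survey, tracker readings cannot be altered by recall, and the protocol does not name the survey score as the primary exposure. This stands too and limits the scope. But section 6.0 does say survey data will be analyzed, and unmonitored children have no other activity record.

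**The survey's content is not described.** Its recall period and respondent are not given. That it asks about activity before the visit is an inference, though a natural one for a survey handed out at follow-up.

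**The figures are close to an upper case.** They assume that every displaced child's family knew the result and shifted the same way. Shifts in opposite directions would partly cancel, and some children also have tracker data. This stands: the table shows what a shift would do, not how likely one is.

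**Analysis could deal with it.** It would be too strong to say that nothing can be done afterwards. Reports from visits before displacement was detected can be used alone. But without a fixed order, the report from the detection visit, which would cover the interval just before displacement was found, is the one that cannot be trusted.

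**Conclusion.** The point holds in a limited form. Section 6.0 collects the activity survey and the outcome film at the same visits and leaves their order open, so reported activity may depend on a known outcome. The exposure to bias is confined to survey-based analyses of activity against loss of reduction, chiefly in children without a monitor, and to the aim on reporting accuracy.

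Under the assumptions stated, the nominal 5% error rate could rise to somewhere between about 10% and 63%, depending on the assumed shift (0.2 to 0.5 SD) and on whether 50 or 100 children are enrolled, at 30% displaced. With no shift it stays at 5%. The textual gap does not depend on these numbers, and they should not be read as an estimate of the actual bias. This is a cheap improvement to data collection, not a contradiction in the protocol.

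**What to change.** Add one sentence to section 6.0, for example: *The activity survey is completed at check-in, before that visit's x-ray is taken or discussed, and its completion time is recorded.*

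For survey-based analyses of activity against displacement, use for each child only the activity reported up to and including the visit at which displacement is first detected, and compare displaced and non-displaced children over the same follow-up interval. This is needed because the check-in survey protects only the visit at which displacement is found; at later visits the family already knows. Simply dropping every survey completed after disclosure would be a poor substitute: it would remove reports in a way that depends on the outcome and leave unequal observation windows.

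Cost: a minor change to clinic flow, with the same instrument at the same visit. Later surveys from children with known displacement would not be used in that analysis.
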